We will examine patient and implementation outcomes of depression screening and group interpersonal therapy for adolescents (IPT-A) compared to treatment as usual in a pilot cluster randomized trial at four primary care clinics (PCC). Two PCC will be randomized to routine screening and IPT-A (intervention) and the other two PCC will be randomized to treatment as usual (TAU). In the IPT-A arm, providers (nurses and/or medical technicians) at PCCs will be trained to conduct paper-based depression screening as part of routine clinical care. Two providers (nurses and/or medical technicians) per clinic will be trained to facilitate group IPT-A. In the TAU arm, primary care providers will continue referring adolescents to specialized mental health services per existing protocol (when they believe the adolescent is struggling with a mental health problem or when the adolescent/their caregiver requests a referral to mental health services). Treatment providers in the TAU arm are the Psychiatric Technicians and psychologists at primary care clinics to whom adolescents are currently referred.

Study procedures

In the treatment study arm, we are evaluating the impact of IPT-A on depression symptoms in adolescents as well as the feasibility and acceptability of its introduction in primary care clinics. Therefore, adolescents identified as having depression, via screening on the PHQ-A, will be referred to IPT-A treatment groups instead of being referred to Psychiatric Technicians and psychologists in Mental Health Services at the PCC who provide unstructured psychotherapy (TAU).

IPT-A (Treatment) Study Arm: Prior to initiation of the pilot study, we will train providers at the PCC in the IPT-A arm to screen for depression using the Patient Health Questionnaire for

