Adolescents (PHQ-A). Training will include didactics and role-plays to practice administration of the PHQ-A with corrective feedback and evaluations. Two providers per PCC will be selected to be trained on delivery of group IPT-A. Training will occur via an apprenticeship model which includes trainers (i.e., non-local experts in the mental health intervention), supervisors (i.e., local individuals chosen for an advanced role), and counselors (i.e., local individuals who provide the interventions). A group IPT-A training expert will train two psychologists from the MoH. Following this, the MoH psychologists will train the two staff members at the IPT-A arm PCC to facilitate group IPT-A. The MoH psychologists will supervise PCC providers for an additional 3 months to achieve competency prior to pilot trial initiation.

Every adolescent who attends PCCs will be screened for depression as part of their routine clinical care. Providers will use the PHQ-A for screening. Using a script, trained research assistants will introduce the study to adolescents who screen positive for depression and their caregivers. If interested, research assistants will collect patient demographic data (age in years, gender) on a questionnaire to verify eligibility.

Group IPT-A begins with one individual session, followed by ten group sessions, and ends with one individual session. As part of each Group IPT-A session, providers will collect data from adolescents on depression symptoms using the PHQ-A at treatment initiation, 6 weeks after treatment initiation (treatment midpoint), 12 weeks after treatment initiation (end of treatment), and 24 weeks after treatment initiation (3-month follow-up). The Project Coordinator will call adolescents who do not enter or who discontinue treatment to arrange data collection at these time points. For adolescents who do not enter treatment, the first scheduled session will be considered the “treatment initiation” timepoint.

Data on treatment fidelity will be collected via the Group IPT-A Fidelity Checklist, completed by the local IPT-A trainers at 10 randomly-selected sessions for each provider. On the Fidelity Checklist, providers are scored for low (1), moderate (2), or high (3) adherence to each essential element of treatment, and fidelity is measured by the total score.

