Post Treatment Data Collection: After the final treatment session (either full course of treatment or after the adolescent discontinues treatment), research assistants will conduct semi-structured exit interviews with participating adolescents and their caregivers (IPT-A arm only), which will be digitally audio-recorded, to collect feedback on acceptability and appropriateness of the depression care they received. Research assistants will also conduct exit interviews, which will be digitally-audio recorded, with PCC providers (IPT-A arm only) after the completion of the pilot trial period to collect feedback on acceptability and appropriateness of depression care they provided. Data on treatment penetration (number adolescents entering treatment/ number referred), feasibility (retention in treatment, measured as number of treatment sessions completed/number of planned treatment sessions), and sustainability (penetration and retention in the 6 months following trial end) will be collected by research assistants from clinic records (both study arms).

STATISTICAL PROCEDURES

Quantitative analysis: Power was calculated conservatively based on participation of 90 adolescents, anticipating possible loss-to-follow up of ~10% as seen in similar trials (Bolton, Bass et al. 2007, Murray, Skavenski et al. 2015). Assuming an intra-PCC correlation coefficient of 0.02-

0.10,(Hemming, Girling et al. 2011) we will have 80% power to detect a moderate 0.6 to large >1.0 effect size of continuous outcomes using a two-sided z-test with an alpha level of 0.05. All analyses between arms will be based on intention to treat. Symptom change between baseline and treatment midpoint, treatment end, and 3- month follow-up will be compared in the IPT-A versus TAU study arms through mixedmodels linear regression analysis, treating PCC as a random effect and baseline symptoms and treatment arm as fixed effects. Subsequently, patient age and gender will be introduced into the model as independent fixed effects to adjust for their potential effect on symptom change. Similar analyses will be used to compare penetration, retention, and sustainability across arms. Within each arm, I will conduct exploratory analyses of the effect of adolescent age and gender on symptom change as well as provider age, gender, and years working in PCCs on fidelity to treatment using linear regression.

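### The exploratory regression of fidelity on provider age, gender and years in PCCs rests on four providers and cannot give usable inference; report fidelity descriptively instead

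*Combined protocol and SAP*

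**What the plan says.** Under STATISTICAL PROCEDURES, Quantitative analysis, the last sentence reads in part "Within each arm, I will conduct exploratory analyses of the effect of adolescent age and gender on symptom change", and then adds to the same exploratory analyses the effect of "provider age, gender, and years working in PCCs on fidelity to treatment using linear regression".

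The number of providers is not stated there. It follows from STUDY DESIGN, which allocates two of the four clinics to IPT-A and says "Two providers (nurses and/or medical technicians) per clinic will be trained to facilitate group IPT-A". The IPT-A (Treatment) Study Arm text repeats this: "Two providers per PCC will be selected to be trained on delivery of group IPT-A".

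The same section describes the outcome. The Group IPT-A Fidelity Checklist is "completed by the local IPT-A trainers at 10 randomly-selected sessions for each provider", and "fidelity is measured by the total score". No fidelity measure is described for TAU.

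For this analysis the plan does not give the unit (provider or session), a term for repeated ratings of the same provider, or whether the three characteristics enter jointly or singly. The PCC random effect is specified for the between-arm models, not for this regression.

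**The concern.** Age, gender and years of service are properties of the provider, so the information about their effect comes from differences between providers, and there are four. Rating each provider 10 times sharpens that provider's mean but adds no providers.

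The choice the plan leaves open therefore matters. Depending on how the sentence is carried out, the analyst gets no test, an almost uninformative test, or a test with too many false positives. The last is the most hazardous, because software will return 36 nominal residual degrees of freedom and ordinary-looking p-values without warning.

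The study intends its findings to inform scale-up. A spurious statement that age, gender or experience predicts fidelity could influence who is chosen to deliver IPT-A. A null result could equally be misread as showing that provider characteristics do not matter.

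**Working it through.** The plan gives no sample size, power or alpha for this analysis, so there is no stated figure to reproduce. The two-sided 0.05 level used below is borrowed from the power statement ("using a two-sided z-test with an alpha level of 0.05").

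**Inputs**
- IPT-A clinics: 2 (STUDY DESIGN).
- Facilitators per clinic: 2 (STUDY DESIGN, and again in the IPT-A arm procedures). Providers: 2 × 2 = 4.
- Ratings per provider: 10 (IPT-A arm procedures). Ratings: 4 × 10 = 40.
- Predictors: 3, all at provider level (Quantitative analysis).
- Within-provider correlation of ratings (ICC): not in the documents; assumed over 0 to 0.3.

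**Reading 1: provider means, three predictors together.** Coefficients: 1 + 3 = 4. Residual df: 4 − 4 = 0. The fit is perfect whatever the data, and no standard error, interval or p-value exists.

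**Reading 2: provider means, one predictor at a time.** Residual df: 4 − 2 = 2, and t(0.975; 2) = 4.303.
- Critical |r| = t/√(t² + df) = 4.303/√(4.303² + 2) = 0.950.
- Power, from 200,000 simulated bivariate normal samples of size 4: 9.5% at a true correlation of 0.5, 17% at 0.7 and 44% at 0.9.
- Approximate 95% interval for an observed r of 0.7 (Fisher): tanh(0.867 ± 1.96/√(4 − 3)) = −0.80 to 0.99.
- Gender split two against two: t = difference/(s√(1/2 + 1/2)) = difference/s, so the difference must exceed 4.3 pooled SDs of provider means.

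**Reading 3: 40 session ratings, ordinary regression, no provider term.** In the joint model each coefficient is a linear combination of the four provider means. Ordinary regression takes the variance of a provider mean as the within-provider variance divided by 10; the true variance also includes the between-provider variance. The ratio of true to assumed variance is

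V = 1 + 10 × ICC/(1 − ICC).

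Nominal residual df are 40 − 4 = 36 and t(0.975; 36) = 2.028. The false-positive rate per coefficient is P(|t₃₆| > 2.028/√V). The last column is from about 20,000 simulated null datasets per ICC, with age as the single predictor.

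| ICC | V | Joint model | One predictor at a time |
|---|---|---|---|
| 0 | 1 | 5% | 5% |
| 0.02 | 1.204 | 7% | 7% |
| 0.05 | 1.526 | 11% | 10% |
| 0.1 | 2.111 | 17% | 16% |
| 0.2 | 3.5 | 29% | 26% |
| 0.3 | 5.286 | 38% | 34% |

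In a separate simulation of the joint model (5,000 runs per ICC), the chance of at least one false positive among the three coefficients was about 11%, 21%, 33% and 62% at ICC 0, 0.05, 0.1 and 0.3.

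**Adding a provider random effect.** This does not rescue the joint model: the intercept and three predictors already use all four provider-level degrees of freedom.

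**The case against.** The strongest reply is that the plan calls the analysis exploratory, in a pilot, and attaches no hypothesis, alpha or decision rule to it. Low power in an exploratory analysis is not an error, and one predictor at a time on provider means is a valid test under normality. A lighter edit would name the provider as the unit, fit single predictors, and report estimates with intervals as hypothesis-generating.

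Much of this stands. The consequence is limited, and the single-predictor model can be fitted. But the exploratory label does not create residual degrees of freedom, and it does not correct an anti-conservative test. The lighter edit would be legitimate, but an interval such as −0.80 to 0.99 tells the reader nothing that a plot of four providers does not.

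Two further points are fair:

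- The excess false positives under reading 3 depend on an assumed ICC; at ICC 0 the rate is the nominal 5%. The joint session-level model is also a valid comparison of these four particular providers. What it cannot do is attribute their differences to age, gender or years of service.
- The count of four is derived. One sentence on training in the IPT-A arm could be read as two facilitators in total. That would make matters worse, since a single predictor would then leave 2 − 2 = 0 df. Staff turnover might add a provider or two, but the documents do not plan for it.

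**Conclusion.** The concern holds. With four providers, no natural reading of the planned regression gives usable inference. The joint model on provider means has 0 residual df. Single predictors need |r| of at least 0.95 and have power of 9.5% and 17% at true correlations of 0.5 and 0.7. Session-level regression without a provider term has a per-coefficient false-positive rate of 5% to 38% (joint) or 5% to 34% (single) for ICC from 0 to 0.3.

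These figures assume two facilitators at each of two clinics, 10 ratings each, a two-sided 0.05 level, normal data and the ICC range shown. The strict statement that no test exists applies only to reading 1; for reading 2 the limitation is practical.

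The effect is confined to what may be said about provider characteristics and fidelity. As a drafting point that changes no result, the opening within-arm qualifier also covers fidelity, which is measured in one arm only.

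**What to change.** Replace the provider-characteristic regression with text such as:

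> Fidelity will be reported descriptively in the IPT-A arm only: mean and range of the total score per provider and per clinic, with session scores plotted by provider. Any association with provider age, gender or years in PCCs will be shown without p-values.

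Limit the within-arm qualifier to the adolescent symptom-change analyses.

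The cost is one sentence in the analysis plan and no new data. A planned exploratory test is dropped, so the trial will report no formal result on provider characteristics and fidelity. With four staff in two clinics, individuals could also be recognised from scores set beside age, gender and years of service, so public reports need care over how much of this is shown together.
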